## Statistical Methods

This study will quantify the relative specificity, sensitivity, positive and negative predictive values, and accuracy of 1) an AP image alone, 2) a LAT image alone, and 3) AP and LAT images together. The results will be analyzed to determine effects of demographic and surgical variables. The McNemar test and generalized linear mixed models will be used as statistical tools [Hellbach 2018].

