## **INTRAOPERATIVE RADIOGRAPHIC DETECTION OF RETAINED SURGICAL SPONGES**

### **OBJECTIVE**

The aim of this prospective study is determine the efficacy of intraoperative x-ray to rule out retained surgical sponges.

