### **BACKGROUND**

Retained surgical sponges can be result in serious medical morbidities such as infection, pain, abscess and contribute to medicolegal problems. In a retrospective control study with nearly two hundred thousand surgeries, the retained foreign object rate was found approximately 1/5500 [Cima 2008]. Sponges were the most common items left behind [Lincourt 2007]. Even though there are strict protocols to account for every surgical sponge used during a procedure, human error is not zero. When a retained surgical sponge is suspected, intraoperative x-ray images can be obtained to rule out a foreign body [Turgut 2018]. One radiographic image of the surgical field is most commonly preferred. However, a retained surgical sponge may not appear on intraoperative x-rays. The aim of this study is to determine how sensitive and specific x-rays are for detecting retained surgical sponges. Another aim of this study is determine if two views of the surgical field improve detection of retained sponges and may decrease false negative rates.

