### **METHODS**

#### **Study Design**

This is a prospective, randomized study with two cohorts: one experimental and one control. Anteroposterior (AP) and lateral (LAT) radiographs are routinely obtained as standard of care during spine surgery to confirm proper implant placement. These images will be used in this study. In one-half of the study subjects, a surgical sponge will be intentionally placed in the surgical field prior to imaging. Postoperatively, three spine surgeons (Fellows of Twin Cities Spine Center) who did not participate in the surgery will assess the images for the presence or absence of a retained surgical sponge.

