#### **Sample Size**

Our hypothesis for statistical analysis is that there will be 90% sensitivity/specificity [Revesz 1983]. For a 95% confidence interval with  $p=0.05$ , a sample size of  $n=146$  is estimated [Jones 2003].

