### **Randomization**

Randomization will be performed prior to surgery using sealed envelopes. One hundred forty six (146) envelopes will be sequentially numbered and 146 chits with either the number “1 (retained sponge, n=73) or the number “2” (no retained sponge, n=73) will be prepared. Chits will be drawn at random and sequentially placed in the envelopes, which will be sealed. For each consented subject, when surgery is scheduled, an envelope will be opened and the surgery worksheet annotated, as appropriate.

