## **INTENDED USE OF THE DATA**

The study investigators may publish the results of the study in medical journals and society meetings. The study investigators may use the results to modify the Standard of Care.

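### Planned PPV and NPV will hold only at the 50% sponge prevalence set by randomization, because the plan names no target prevalence and no conversion

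*Combined protocol and SAP*

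**What the plan says.** All references are to the combined protocol and SAP.

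- **Statistical Methods** lists the measures: "This study will quantify the relative specificity, sensitivity, positive and negative predictive values, and accuracy", for three image sets: the AP image alone, the lateral image alone, and both together. The only tools it names are the McNemar test and generalized linear mixed models.
- **Study Design** sets the fraction of films with a sponge: "In one-half of the study subjects, a surgical sponge will be intentionally placed in the surgical field prior to imaging".
- **Randomization** makes the split exact, with 73 chits for each group. The control lot reads "no retained sponge, n=73) will be prepared".
- **Sample Size** gives the only performance figures: "Our hypothesis for statistical analysis is that there will be 90% sensitivity/specificity".
- **Objective**: the study is to "determine the efficacy of intraoperative x-ray to rule out retained surgical sponges".
- **Background** describes the clinical use: "When a retained surgical sponge is suspected, intraoperative x-ray images can be obtained to rule out a foreign body". It also cites a rate of about 1/5500 for retained foreign objects across surgeries.
- **Intended Use of the Data**: "The study investigators may use the results to modify the Standard of Care".

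No section states a prevalence for suspected cases, a conversion of predictive values to another prevalence, or a label limiting them to the design prevalence.

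**The concern.** Sensitivity and specificity are each calculated within one arm, so the allocation ratio does not enter them. PPV and NPV are calculated across arms and depend directly on the proportion of subjects with a sponge. Here that proportion is one half only because the randomization made it so. Nothing in the document suggests that half of clinically suspected cases have a retained sponge.

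NPV, or its complement the residual risk after a negative film, answers the rule-out question most directly. If clinical prevalence is below 50%, an unlabelled table value overstates that residual risk and overstates PPV, so that too few false alarms would be expected. Since the investigators may use the results to change practice, the basis of these figures should be stated.

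**Working it through.** **Inputs.** Allocation 73 and 73 (Randomization). Sensitivity Sn = 0.90 and specificity Sp = 0.90 (Sample Size). Prevalence p in suspected cases is not given, so a range of 1% to 30% is assumed.

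**Design prevalence.** 73/146 = 0.50, which matches the one-half in Study Design.

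**Formulas.**
- PPV = Sn·p / [Sn·p + (1−Sp)(1−p)]
- Residual risk after a negative film = 1 − NPV = (1−Sn)·p / [(1−Sn)·p + Sp(1−p)]
- Accuracy = Sn·p + Sp(1−p)

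**Results at Sn = Sp = 0.90.**

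| p | PPV | Residual risk | NPV |
|---|---|---|---|
| 50% (trial table) | 0.45/(0.45+0.05) = 90% | 0.05/(0.05+0.45) = 1 in 10 | 90% |
| 30% | 0.27/(0.27+0.07) = 79% | 0.03/(0.03+0.63) = 1 in 22 | 95.5% |
| 20% | 0.18/(0.18+0.08) = 69% | 0.02/(0.02+0.72) = 1 in 37 | 97.3% |
| 10% | 0.09/(0.09+0.09) = 50% | 0.01/(0.01+0.81) = 1 in 82 | 98.8% |
| 5% | 0.045/(0.045+0.095) = 32% | 0.005/(0.005+0.855) = 1 in 172 | 99.4% |
| 1% | 0.009/(0.009+0.099) = 8.3% | 0.001/(0.001+0.891) = 1 in 892 | 99.9% |

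The table PPV is too high by a factor of 90/79 = 1.1 at 30%, 90/50 = 1.8 at 10% and 90/8.3 = 10.8 at 1%.

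**Other assumed performance, at p = 10%.** With 85%/85%, PPV is 0.085/(0.085+0.135) = 39%, against 85% in the table. With 95%/95%, it is 0.095/(0.095+0.045) = 68%, against 95%.

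**Precision at the planned size.** Take one reader with 66 of 73 correct in each arm (90.4%). LR+ = 66/7 = 9.43 and LR− = 7/66 = 0.106. Each log-LR has standard error √(0.0959/66 + 0.9041/7) = 0.361. The 95% limits are 4.64 to 19.15 for LR+ and 0.052 to 0.215 for LR−. Multiplying by the prior odds p/(1−p) and converting back to probabilities gives:

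| p | PPV (95% CI) | NPV (95% CI) |
|---|---|---|
| 50% | 90.4% (82.3 to 95.0) | 90.4% (82.3 to 95.0) |
| 10% | 51% (34 to 68) | 98.8% (97.7 to 99.4) |
| 5% | 33% (20 to 50) | 99.4% (98.9 to 99.7) |
| 1% | 8.7% (4.5 to 16.2) | 99.89% (99.78 to 99.95) |

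At 20% the PPV interval is 53.7 to 82.7, which just overlaps the table interval. At 10% or below the two do not overlap, so the shift is larger than the sampling uncertainty.

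**What does not move.** PPV rises with LR+ and NPV rises as LR− falls, at any p. The ranking of the three image sets on each is therefore the same at every prevalence, and only the size of the differences changes. Accuracy at 90%/90% is 0.90p + 0.90(1−p) = 90% throughout. It moves only if sensitivity and specificity differ: at an assumed 95%/85% it is 90.0% at p = 50% and 0.0095 + 0.8415 = 85.1% at p = 1%.

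**The case against.** The strongest reply is that the plan promises relative measures across image sets and never says that PPV and NPV will be read off the raw table or presented as clinical values. The aim in Background and the sizing in Sample Size rest on sensitivity and specificity, which are sound here. For a rule-out objective, the table NPV errs in the cautious direction. The most striking ratios concern PPV, and all the sizes depend on an assumed prevalence. Each of these points is correct, and together they keep this a minor matter. They do not remove it: the section commits to quantifying PPV and NPV, and from these data without a conversion those quantities are fixed by the allocation ratio.

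A reader might infer three stronger things that the document does not support.

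- *That accuracy is equally tied to 50%.* At the only performance values the plan states, it does not change with prevalence. Converting it to low prevalence would also help little: at 1%, 99% of its weight falls on specificity, so it becomes nearly blind to missed sponges.
- *That the cited 1/5500 is the right prevalence.* At 90%/90% it would give PPV 0.9/(0.9 + 0.1 × 5499) = 0.16%. But that rate covers all retained foreign objects across surgeries, whereas the film is described for suspected cases, where prevalence may be much higher.
- *That the comparison of one view with two is invalid.* The PPV and NPV rankings, and the sensitivity and specificity comparisons, do not depend on the 50% split.

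**Conclusion.** The point holds for PPV and NPV and is a free improvement. Values taken directly from the trial table apply only at 50% prevalence, and the plan neither says so nor provides a conversion. At 90%/90%, the stated residual risk of 1 in 10 would be 1 in 22 at 30% prevalence and 1 in 82 at 10%, while PPV would fall from 90% to 79% and 50%.

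These sizes rest on two assumptions: a clinical prevalence that the document does not give, and sensitivity and specificity for deliberately placed sponges that carry over to suspected retained ones. The intervals shown are for one reader, whereas the plan has three readers of the same images. For accuracy the point is conditional on sensitivity and specificity differing.

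**What to change.** Add to Statistical Methods:

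> PPV and NPV for AP, LAT and AP+LAT will be derived by Bayes' theorem from the estimated sensitivity and specificity over a stated and justified range of assumed prevalences (for example 1%, 5%, 10%, 20% and 30%), with 95% confidence intervals carried through from sensitivity and specificity estimates that account for the three readers of the same images. This assumes that sensitivity and specificity for deliberately placed sponges carry over to suspected retained sponges. Accuracy, and any PPV or NPV taken directly from the trial table, will be labelled as applying at the design prevalence of 50%.

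The investigators should choose the range and give their reasons. LR+ and LR− may be added as supportive measures.

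The cost is three sentences and a few lines of analysis, with no new subjects, images or reads.

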### **Data Collection**

Demographic information will include sex, age, height, and weight. Surgical information will

include the number of levels decompressed and instrumented, type and configuration of instrumentation, use of bone graft and/or biologics, estimated blood loss, and length of surgery. Radiographic images will include AP and LAT views of the surgical field prior to closing.

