## Methods

For subjects in study group 1, the following will happen:

- OR staff will count surgical sponges, as is routine.
- AP and Lateral radiographic images will be taken of the surgical field. (This is Standard of Care, because radiographic images are taken for all patients to confirm correct placement of the instrumentation.
- Just prior to imaging, the surgeon will purposely place a sponge in the wound. He will state this to the circulating nurse and scrub tech.
- After imaging, the surgeon will remove the sponge. He will state that he has removed the sponge; the scrub tech will confirm that the sponge has been removed; the circulating nurse will note this in your chart.
- OR staff will re-count surgical sponges to be certain none are left in the wound.

For subjects in study group 2, the following will happen:

- Two radiographs will be taken of the spine (AP and Lateral views) to verify that the instrumentation is placed properly.
- OR staff will re-count surgical sponges to be certain none are left in the wound.

For all subjects:

Images will be stored on Allina's medical record system. Three investigators (TCSC Fellows, TBD) not participating in the surgery will independently view the images and note if a retained sponge is visible on either image or both.

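### Is the analysis of patient and operative variables too loosely specified, given how few reading errors are expected?

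*Combined protocol and SAP*

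**What the plan says.** The Statistical Methods section first sets out the main task: predictive values, sensitivity, specificity and "accuracy of 1) an AP image alone, 2) a LAT image alone, and 3) AP and LAT images together". One sentence on covariates follows: "The results will be analyzed to determine effects of demographic and surgical variables". The section then names the McNemar test and generalized linear mixed models as tools. It does not link either tool to the covariate sentence or list any model terms.

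The variables can only be inferred from Data Collection. The patient items are given as "Demographic information will include sex, age, height, and weight". The operative items are "number of levels decompressed and instrumented, type and configuration of instrumentation, use of bone graft and/or biologics, estimated blood loss, and length of surgery".

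The Background gives the main aim: "The aim of this study is to determine how sensitive and specific x-rays are for detecting retained surgical sponges". Its second aim is whether two views improve on one. Neither the Objective nor the Background asks which patients or operations are harder to read. The Sample Size section rests only on accuracy: "Our hypothesis for statistical analysis is that there will be 90% sensitivity/specificity". Under Methods, three fellows who took no part in the surgery "will independently view the images and note if a retained sponge is visible on either image or both".

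**The concern.** Taken literally, the covariate sentence promises to establish effects, yet it does not say of which variables, on which outcome (misses, false alarms or overall accuracy) or for which view. If everything in Data Collection is meant, there are 9 variables, or 12 when paired items are split, and only a handful of reading errors to explain.

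Two harms could follow. Testing many variables at 0.05 makes a chance predictor likely. A real predictor could also be missed because the errors are sparse. The section on intended use of the data allows results to influence routine practice, so an over-read covariate finding could have consequences.

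**Working it through.** **The plan's own figure.** The plan gives no figure for the covariate analysis. Its only sample-size figure is 146. If the 0.05 in Sample Size is read as a half-width, 1.96² × 0.90 × 0.10 / 0.05² = 138.3, so 139. Dividing 138.3 by 0.95 gives 146, but the plan states no 5% loss. The counts below use the 73 and 73 in Randomization directly, so this gap does not affect them.

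**Variables (Data Collection).** There are 4 patient items. The operative items number 5 if each pair counts once and 8 if levels, instrumentation and graft/biologics are each split. The total is 9 to 12.

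**Expected errors at 90% sensitivity and specificity (Sample Size, Randomization).**
- Misses per reader: 73 × 0.10 = 7.3. False alarms: also 7.3.
- All errors per reader: 146 × 0.10 = 14.6.
- Three readers pooled: 3 × 7.3 = 21.9 misses; 3 × 14.6 = 43.8 errors.
- The three readers share each subject, so the design effect is 1 + 2ρ. With ρ assumed at 0.3, 21.9/1.6 = 13.7 effective misses; at 0.5, 21.9/2.0 = 10.95. For all errors the figures are 27.4 and 21.9.
- The 90% is not tied to a view. At 80% to 85% sensitivity, misses per reader would be 14.6 to 11.0; at 95%, about 3.7.

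**Errors per variable, if every variable were fitted together.** For misses, from 7.3/12 = 0.6 (one reader, 12 variables) to 21.9/9 = 2.4 (pooled, 9 variables). For accuracy, from 14.6/12 = 1.2 to 43.8/9 = 4.9. A joint fit of that size would be unstable.

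**Chance findings, if every variable were tested at 0.05.** For independent tests, 1 − 0.95⁹ = 0.37 and 1 − 0.95¹² = 0.46. If the tests correlate 0.5, the figures are 0.27 and 0.32. All are per outcome. Two independent tests would give 1 − 0.95² = 0.10.

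**Power for one variable, pooled over readers, at ρ = 0.5 and 0.3.**

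| Contrast | Outcome | ρ = 0.5 | ρ = 0.3 |
|---|---|---|---|
| 15% v 5% error, even binary split | misses | 41–43% | 50–52% |
| 15% v 5% error, even binary split | accuracy | 70–72% | 79–81% |
| Continuous, odds ratio 2.0 per SD | misses | about 54% | about 64% |
| Continuous, odds ratio 2.5 per SD | misses | 73–74% | about 83% |
| Continuous, odds ratio 2.0 per SD | accuracy | about 84% | about 90% |

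The binary rows come from a normal approximation and a beta-binomial simulation. The accuracy row for the binary split supposes the same difference in misses and false alarms. The continuous rows come from simulation with 10% mean error. The odds ratios and correlations are assumptions. Six of the nine items (age, height, weight, number of levels, blood loss, length of surgery) are continuous or counts, so the continuous rows apply to most of the list.

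**Effect of a shorter list.** With two predictors, effective misses per predictor would be 10.95/2 = 5.5 to 13.7/2 = 6.8. The power figures above are already for one variable at a time, so a shorter list leaves them unchanged.

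**The case for a change.** The strongest case for acting is that the plan sets no limit. Without a named outcome, view or predictor list, all three can be chosen after the reads are in. The 37% to 46% is per outcome and does not count that freedom. Repeating 9 to 12 independent tests on each of the three views would give 1 − 0.95²⁷ = 0.75 to 1 − 0.95³⁶ = 0.84, although the views share subjects and readers, so this overstates the risk. Fixing it would need only a few lines of text. If the analysis is exploratory, the plan could say so.

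Part of this stands. The gap is real, and the plan does not supply the label. A joint fit of all variables would be unreliable, and a moderate difference in misses across a binary split has only about even odds of being found.

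The rest depends on conditions the plan does not set. It nowhere says that every collected variable will be tested, and Data Collection could equally serve a baseline table. It sets no 0.05 rule for this analysis. The word the concern leans on carries little weight, since the Objective and Background use the same verb loosely for their own aims. The passage on changing practice speaks of the study's results in general and does not mention covariate findings.

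**Conclusion.** No change to the plan is needed. The covariate sentence leaves out detail about a secondary analysis, and analysts can fill that gap sensibly: a mixed model accounting for subject and reader, few variables at a time, with estimates and intervals reported. The aims contain no predictor question, so the results would be read as exploratory even without the label.

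If all 9 to 12 variables were each tested at 0.05, the chance of at least one false predictor would be 37% to 46% for independent tests, or 27% to 32% with correlation 0.5. That is a reason for caution in reporting and does not show that the planned analysis is wrong. The number of reading errors limits power for any one variable, and prespecifying a short list would not alter that number.

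Sensitivity, specificity and predictive values do not depend on the covariate models. The McNemar comparison of views is made within subject, so subject-level covariates are the same on both sides. The conclusion rests on the plan's 90% assumption, on 73 subjects per group and on assumed between-reader correlations of 0.3 to 0.5.

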## **RISK/SAFETY INFORMATION**

This study presents no additional risk to subjects associated with the radiographs because two x-rays of the surgical field are obtained as the standard of care. If the subject is of child bearing potential, the PI will have already discussed the risks of lumbar spine surgery, which includes the use of radiographs.

A count of sponges will be performed before and after the sponge is placed in the imaging field to ensure the sponge is removed. (Counting is the standard procedure [AORN 2018].); the subjects are not at greater risk from the radiographs.

There is no additional risk to surgeons as the two radiographs are the standard of care.

## **STUDY OVERSIGHT**

The protocol, informed consent document and relevant supporting information will be submitted to the IRB for review and must be approved before the study is initiated. This study will be conducted in accordance with the ethical principles that have their origin in the Declaration of Helsinki and that are consistent with Good Clinical Practice and applicable regulatory requirements. The study will be conducted in accordance with the regulations of the United States Food and Drug Administration (FDA) as described in 21 CFR 50 and 56 [add 312 for IND studies or 812 for device studies], applicable laws and the IRB requirements. A protocol change intended to eliminate an apparent immediate hazard to subjects may be implemented immediately provided the IRB is notified within 10 working days.

It will be the responsibility of the investigator to provide each subject with full and adequate verbal and written information using the IRB-approved informed consent document, including the objective and procedures of the study and the possible risks involved before inclusion in the study. Informed consent will be obtained prior to performing any study-related procedures, including screening and changes in medications including any washout of medications. A copy of the signed informed consent will be given to the study subject.

Study data will be made available for monitoring, auditing, IRB review and regulatory inspection by providing direct access to study related source data. The study may be prematurely closed for administrative reasons by the Principal Investigator (for example, lack of enrollment, lack of adequate research staffing, lack of adequate funding). The study

may be prematurely by the safety monitors based on study progress or adverse events.

## **CONFIDENTIALITY**

Data will be stored on TCSC computers, which are linked by Allina Health servers. No data will be physically removed from TCSC. The United States Food and Drug Administration may inspect all records related to the study. The IRB and/or other regulatory authorities (for example, the United States Food and Drug Administration) will have access to study-related medical records. Study-related records identifying the subject will be kept confidential and, to the extent permitted by applicable laws and/or regulations will not be made publicly available. If any results of the study are published, the subject's identity will remain confidential.

